## F. OBJECTIVES

### F.1. PRIMARY AIM OF THE KETAMINE-BREXPIRAZOLE TRIAL

The primary objective is to investigate whether the degree of improvement in SDQ total score on brexpiprazole (initial dose .5 mg/day titrating to 3 mg/day over 21 days) is superior to placebo when combined with intranasal ketamine in the acute treatment of patients with TRD at two weeks (Day 14), when added to ongoing and stable antidepressant therapy with respect to the study primary outcome measure. Superiority will be demonstrated by a statistically significant greater decrease ( $p < 0.05$ , 2-sided) on the SDQ total score for patients receiving brexpiprazole versus placebo therapy.

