## G. STUDY DESIGN

### G.1. OVERVIEW

This is a multi-site, double-blind, placebo-controlled study of the acute efficacy of oral brexpiprazole or placebo combined with intranasal ketamine added to ongoing, stable, and adequate antidepressant therapy (ADT) in the treatment of adults with MDD with TRD. Adequate ADT is defined as a therapeutically sufficient dose for a sufficient treatment period, which would be expected to be effective as listed in the MGH ATRQ.

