## N. DATA ANALYSIS

To analyze the primary outcome data, we will use a linear mixed model for the observations taken at baseline, and subsequent visits, with terms for visit, and visit\*treatment for visits other than baseline, the primary contrast of interest being the difference between the two weeks (Day 14) value for active treatment and placebo. To address missing data, we will use all available data and use a restricted maximum likelihood estimation procedure, as implemented by SAS Proc MIXED. The model will include a site, a site\*time effect and a site\*time\*treatment interaction. The latter will be removed if not significant. Number of comorbid medical and psychiatric disorders and duration of illness, as measured prior to randomization, will be included as covariates. For the continuous secondary efficacy variables, the same approach as for the primary efficacy variable will be used for the analysis.

Power analysis: the sample size was chosen to ensure 80% power to detect an effect size of 0.8 on the SDQ between brexpiprazole plus intranasal ketamine treatment and placebo at a two-sided 0.05 significance level. This assumes the randomization of 52 subjects (26 subjects per arm).

O. PROTOCOL SIGNATURE PAGE

I have read this protocol and agree to adhere to the requirements. I will provide copies of this protocol and all pertinent information to the study personnel under my supervision. I will discuss this material with them and ensure they are fully informed regarding the conduct of the study according to 21 CFR parts 50, 54, 56 and 812, 45 CFR 46, to GCP as described in ICH guideline E6 and to hospital Institutional Review Boards.

\_\_\_\_\_  
Clinical Site

\_\_\_\_\_  
Principal Investigator Signature

\_\_\_\_\_  
Date

\_\_\_\_\_  
Principal Investigator  
Printed Name

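### Section N lets a significance test decide whether site*time*treatment stays in the primary model, and gives no site weights for the Day 14 contrast if it stays

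*Combined protocol and SAP*

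**What the plan says.** Section N specifies a linear mixed model fitted by restricted maximum likelihood, with visit, post-baseline visit*treatment, site, site*time and site*time*treatment. Of the last term it says "The latter will be removed if not significant". It also states: "Number of comorbid medical and psychiatric disorders and duration of illness, as measured prior to randomization, will be included as covariates". The target is a single quantity, "the primary contrast of interest being the difference between the two weeks (Day 14) value for active treatment and placebo".

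The same rule reaches further than the SDQ: "For the continuous secondary efficacy variables, the same approach as for the primary efficacy variable will be used for the analysis".

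Section F.1 rests the primary claim on one test: "Superiority will be demonstrated by a statistically significant greater decrease", with p below 0.05, two-sided. Section G.1 describes a multi-site study but gives neither the number nor the sizes of sites. The randomization section (I.1.c) refers to a list and mentions no stratification by site. No section gives the level of the removal test, says whether site is fixed or random, or states site weights.

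**The concern.** Two gaps combine. First, the trial's own outcome data decide which of two models yields the primary p-value, at a level nobody has written down. The tested term covers every post-baseline visit, so a site pattern at Day 28 alone could change the Day 14 model.

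Second, with site*time*treatment in the model there is one Day 14 treatment difference per site. A single contrast needs weights, such as equal weight per site or weight in proportion to patients. With similar site sizes the choice hardly matters. With unequal sites it changes the standard error and, if effects truly differ by site, the quantity being estimated. A trial that keeps the term would have to make this choice after outcomes are known, with the primary claim possibly depending on it.

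**Working it through.** **Inputs from the documents.** 52 patients, 26 per arm, effect size 0.8, two-sided 0.05, 80% power (Section N); 10 post-baseline SDQ visits (Tables 2 and 3). **Assumed, because the documents are silent:** site number and sizes, level of the removal test, site weights.

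**1. The plan's own figure.** Normal approximation: n per arm = 2(1.96 + 0.84)²/0.8² = 24.5, so 25. The two-sample t-test needs 25.5, so 26 per arm and 52 in all, with power 80.7%. The stated size reproduces.

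**2. Size of the tested term.** It has (sites − 1) × 10 degrees of freedom: 10 for two sites, 30 for four, 40 for five.

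**3. Why weights matter once the term stays.** With n_j patients per arm at site j and unit SD, the contrast Σ w_j D_j has SE = √(Σ w_j² · 2/n_j).
- Sites of 13/7/4/2 per arm, patient weights: √(2/26) = 0.277.
- Same sites, equal weights: ¼ √[2(1/13 + 1/7 + 1/4 + 1/2)] = ¼ √1.94 = 0.348.
- Near-even sites of 7/7/6/6: 0.277 against 0.278.

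If the true effects at the 13/7/4/2 sites were 0.4/0.8/1.2/1.6, the equal-weight target would be 4.0/4 = 1.00. The patient-weighted target would be (5.2 + 5.6 + 4.8 + 3.2)/26 = 0.72.

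**4. Simulation of the rule at Day 14.** N = 52, unit SD, random 26/26 allocation, 5% F-test of site*treatment at Day 14. The unequal layouts (total patients per site) are 28/14/10, 16/14/10/8/4 and 23/11/8/6/4. The equal layouts have two to six near-equal sites.

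| Quantity | Equal site weights | Patient weights |
|---|---|---|
| Verdict differs from the model without the term, effect 0.8, unequal sites | 1.1%, 1.1%, 1.4% | 0.2-0.3% |
| Same, equal sites | 0.3% or fewer | nearly the same weights |
| Overall type I error, unequal sites | 5.4-5.6% | 4.9-5.3% |
| Null rejection among kept trials, unequal sites | 13-15% | 7-8% |

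The term is kept in about 5% of trials. Among those, with unequal sites and effect 0.8, the two weightings disagree on significance in about 20-26%. As a share of all trials that is 0.05 × 0.20 = 1.0% to 0.05 × 0.26 = 1.3%.

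**5. Sensitivity (equal weights, unequal layouts).**
- 10% test at Day 14: verdict differs in 2.2-2.7%; type I error 5.6-5.8%.
- 5% test over all 10 post-baseline visits: verdict differs in 0.7%, 1.0% and 1.3%; null rejection among kept trials is 6-9%, lower than with the Day 14 test.
- A 1 SD site difference at Day 28 only, none at Day 14, all-visit test: term kept in 7-19% of trials; Day 14 verdict differs in 1.3-3.2%.
- True between-site SD of 0.4: term kept in 9-15%; verdict differs in 1.8-3.5%.

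**Limits.** Trials with an empty site-arm were left out, about 11-13% in the two layouts with a four-patient site. The all-visit check used a complete-data multivariate test in place of the restricted maximum likelihood model.

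**The case against.** The strongest reply is that this is a prespecified check with little effect. Much of that stands. The two-step rule is written down in advance, 0.05 is the only significance level in the documents and so the natural reading for the removal test, and the cost averaged over all trials is small. Most of the harm comes from the missing weights, not from the test: with patient weights in the retained model the verdict hardly ever moves.

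Several stronger readings are tempting, and the documents do not support them.
- A reader might say the Day 14 target is undefined. Section N names one active-versus-placebo difference at Day 14; what is missing is the site weights.
- A reader might say that a trial keeping the term has the model without it as a rival primary result. Under the rule that model is out once the term is significant. The open choice is between weightings within the retained model.
- A reader might conclude that power is really 60-70%. That is the power in the unequal layouts if the retained model with equal weights were fitted in every trial. The rule fits it in about 5% under a common effect.

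It can also be said that stating the level, the status of site and the weights would be enough. That would remove the ambiguity. It would still let an all-visit test on the outcome data choose the Day 14 model, and with 52 patients the test is a weak safeguard: a between-site SD of 0.4 is flagged in only 9-15% of unequal-site trials.

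**Conclusion.** The point holds as a specification gap that should be closed before outcomes are seen. It does not show that the trial is underpowered or that its overall error rate is seriously wrong. With unequal sites, a common effect of 0.8 and a 5% test at Day 14, the rule changes the verdict in about 1.1-1.4% of trials (equal weights) or 0.2-0.3% (patient weights). With equal sites it does so in 0.3% or fewer. Overall type I error is about 5-6%.

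The weight of the point is conditional. If the term is kept and sites are unequal, the primary conclusion depends on an unstated weighting in roughly one trial in five to one in four at the design effect. All these sizes rest on assumed site numbers, site sizes, test level and weights. That the level and the weights are missing rests on the text alone.

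**What to change.** In Section N, remove site*time*treatment and its removal rule from the primary model. Name as primary the model the plan already reaches when the term drops out: visit, post-baseline visit*treatment, site and site*time as fixed effects, and the stated covariates. Use it for the SDQ and the continuous secondary outcomes. Possible wording:

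*The model will include site and site*\**time as fixed effects. The site*\**time*\**treatment interaction and Day 14 treatment differences by site will be reported as supportive analyses and will not change the primary model.*

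The cost is two sentences. The downside is that site heterogeneity is described outside the primary model. The stated N of 52 does not change. If the sponsor prefers to retain the term, it should be kept in every case, with the site weights and the pooling of small sites written down in advance.

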**Statistical Justification:**

The sample size was chosen to ensure 80% power to detect an effect size of 0.8 on the SDQ between brexpiprazole and placebo at a two-sided 0.05 significance level. This assumes 52 subjects (26 subjects per arm).

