## E. STUDY RATIONALE

Primary Aim: The primary objective is to investigate whether brexpiprazole (initial dose .5 mg/day titrating to 3 mg/day over 21 days) is superior to placebo when combined with intranasal ketamine in the acute treatment of patients with TRD at two weeks (Day 14), when added to ongoing and stable antidepressant therapy with respect to the study primary outcome measure [change in the SDQ total score].

Secondary Aim 1: The secondary objective #1 is to investigate whether brexpiprazole (initial dose .5 mg/day titrating to 3 mg/day over 21 days) is superior to placebo when combined with intranasal ketamine in the acute treatment of patients with TRD within 48 hours (Day 2), when added to ongoing and stable antidepressant therapy with respect to the study primary outcome measure [change in the SDQ total score].

Secondary Aim 2: The secondary objective #2 is to investigate whether brexpiprazole (initial dose .5 mg/day titrating to 3 mg/day over 21 days) is superior to placebo when combined with intranasal ketamine in the acute treatment of patients with TRD at four weeks (Day 28), when added to ongoing and stable antidepressant therapy with respect to the study primary outcome measure [change in the SDQ total score].

Secondary Aim 3: The secondary objective #3 is to investigate whether brexpiprazole (initial dose .5 mg/day titrating to 3 mg/day over 21 days) is superior to placebo when combined with intranasal ketamine in the acute treatment of patients with TRD at four weeks (Day 28), when added to ongoing and stable antidepressant therapy with respect to the rates of sustained response [50% or greater reduction in the MADRS total score].

Secondary Aim 4: The secondary objective #4 is to investigate whether brexpiprazole (initial dose .5 mg/day titrating to 3 mg/day over 21 days) is superior to placebo when combined with intranasal ketamine in the acute treatment of patients with TRD at Day 2, Day 14, and Day 28, when added to ongoing and stable antidepressant therapy with respect to the study secondary outcome measures [MADRS, HAMD-6, CGI-S, CGI-I].

Secondary Aim 5: The secondary objective #5 is to characterize the safety and tolerability of brexpiprazole or placebo treatment during the acute, 4-week treatment period.

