### G.2. METHODS

Following a washout period for patients on prohibited psychotropic agents, 52 eligible subjects will be randomly assigned to one of two arms in a 1:1 fashion: brexpiprazole (initial dose .5 mg/day titrating to 3 mg/day over 21 days) or placebo for four weeks in combination with bi-weekly administration of intranasal ketamine (40 mg) for two weeks, followed by weekly administration of intranasal ketamine (40 mg) for two weeks. All subjects will be followed for 28 days to examine the efficacy and tolerability of the study drugs' effects.

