## H. STUDY POPULATION

### H.1. NUMBER OF SUBJECTS

52 subjects will enter the double-blind treatment phase of the study. This trial will be conducted according to the U.S. FDA guidelines and the Declaration of Helsinki. IRB- approved written informed consent will be obtained from all patients before any protocol-specified procedures are carried out. The subjects will be drawn from an outpatient sample of patients with MDD, diagnosed with the use of the Structured Clinical Interview for DSM-5 Axis I Disorders–Patient Edition (SCID-5), currently on an adequate dose of antidepressant therapy, as defined by the MGH ATRQ, for at least 8 weeks, with the dose being stable for at least 4 weeks, and with TRD (see definition below). For entry into the study, all inclusion criteria must be met, and none of the exclusion criteria can be met.

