**TABLE 2– OVERVIEW OF STUDY SCHEDULE**

Screen Visit	Screening Period	V1 / Baseline Visit	V2	V3	V4	V5	V6	V7	V8	V9	V10	V11
Day -28 to Day -7	Taper (opt.) 5 half-lives of excluded psychotropic drug(s)	Day 0	Day 1	Day 2	Day 5	Day 8	Day 11	Day 14	Day 17	Day 21	Day 23	Day 28
		Baseline Assess.	Assess.	Assess.	Assess.	Assess.	Assess.	Assess.	Assess.	Assess.	Assess.	Assess.
		Intranasal Ketamine Admin.	Assess.	Assess.	Intranasal Ketamine Admin.	Intranasal Ketamine Admin.	Intranasal Ketamine Admin.	Intranasal Ketamine Admin.	Assess.	Intranasal Ketamine Admin.	Assess.	Assess.
		Study Drug*	Study Drug*	Study Drug*	Study Drug*	Study Drug*	Study Drug*	Study Drug*	Study Drug*	Study Drug*	Study Drug*	Study Drug*

\*Brexipiprazole or Placebo

Subjects will be screened for eligibility as detailed above. Study participants will be consented prior to the administration of any procedure or wash-out. Following a washout period, under the close supervision and monitoring of the study clinicians, for patients on psychotropic drugs (with the exception of ongoing antidepressant therapy and of ongoing hypnotic therapy), baseline assessment, MGH CTNI remote interview, and re-confirmation that all criteria for entry into the study are met, eligible subjects will be randomly assigned to one of two arms: brexpiprazole plus intranasal ketamine (n=25) or placebo plus intranasal ketamine (n=25). The brexpiprazole dose will be titrated in the following manner: 0.5 mg/day during the first week, at the Visit 5/Day 8 visit, the dose will be increased to 1 mg/day, at Visit 7/Day 14 the dose will be increased to 2 mg/day, and at Visit 9/Day 21, the dose will be increased to 3 mg/day. If the dose escalation is not tolerated, patient can go back to previous dose (fixed-flexible dose escalation). As per Table 2, all subjects will be followed for 28 days to examine the efficacy and tolerability of brexpiprazole plus intranasal ketamine’s effects. The study assessments will be performed at Days 0, 1, 2, 5, 8, 11, 14, 17, 21, 23, and 28 to assess the safety and efficacy of brexpiprazole plus intranasal ketamine compared to placebo plus intranasal ketamine treatment therapy in depressed patients who have demonstrated an inadequate response

to at least 2 adequate antidepressant therapies (ADTs) during the current MDE. Intranasal ketamine (40 mg) will be administered after all the assessments are completed on Days 0, 5, 8, 11, 14, and 21.

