#### I.1.c. RANDOMIZATION

For entry into the study and randomization, all eligibility criteria MUST be met (e.g., all inclusion criteria and no exclusion criteria). Patients who meet inclusion/exclusion criteria at the baseline visit (Day 0) will be randomized in a 1:1 fashion to either brexpiprazole plus intranasal ketamine treatment or placebo plus intranasal ketamine. All subjects will be followed for up to 28 days post randomization in order to examine the efficacy, safety, and tolerability of the study drug as well as the durability of the study drug's effects.

Specifically, patients will return for outcome assessments 24 hours after initiating treatment (Day 1), 48 hours after initiating treatment (Day 2), and then every 3 days after that for 26 days, with end of study visit one week after the last double-blind visit. (See Table 3 for the Study Schedule of the events.)

Patients with a MADRS score below 20 at either the screening or baseline visits will be excluded from further participation in the study. Upon determining at the baseline visit (Day 0) that a patient still meets all entry criteria for the study, the patient will be assigned (by study subject number assigned at consent) to the next randomization slot from the randomization list that will have been generated by the MGH Biostatistician.

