**TABLE 5 - LIST OF EXAMPLES OF PROTOCOL VIOLATIONS**

	Major Protocol Violation	Minor Protocol Violation
The list of examples is intended as a guide and is not all-inclusive.		
Definition	A violation that may :  Impact subject safety,  Affect the integrity of study data, and/ or  Affect the subject’s willingness to participate in the study.	A violation that does not :  Impact subject safety,  Compromise the integrity of study data, and/ or  Affect the subject’s willingness to participate in the study.
Examples  (not all-inclusive)	
Failure to obtain informed consent
 
Informed consent obtained by an unauthorized individual
 
Enrollment of a subject who did not meet eligibility criteria for whom a protocol exception was not obtained
 
Performing a study procedure that is not approved by the IRB and/or is not in the protocol
 
Failure to perform a required lab test that, in the opinion of the Site Investigator, may affect subject safety or data integrity
 
Failure to perform or follow a study procedure that, in the opinion of the Site Investigator, may affect subject safety or data integrity
 
Failure to follow safety (AE) management plan
 
Failure to report a SAE to the IRB and/or Coordination Center
	
Implementation of unapproved recruitment procedures
 
Only a photocopy of the signed/ dated consent form is available (the original is missing)
 
Pages are missing from the signed/ dated informed consent form
 
Use of invalid consent form (i.e., without IRB approval or outdated/expired form)
 
Failure to perform or follow an approved study procedure that, in the opinion of the Site Investigator, does not affect subject safety or data integrity
 
Study procedure conducted out of sequence
 
Failure to perform a required lab test
 
Missing lab results
 
Study Visit out of approved window
 
Over-enrollment

		Enrollment of subjects after IRB approval of the study has expired  Failure to submit a continuing review application to the IRB before study expiration
Reporting Requirements	Record the date discovered, date occurred, description of event in the Protocol Deviation Log.  Notify the Coordinating Center within 24 business hours.	Record the date discovered, date occurred, description of event in the Protocol Deviation Log.  Notify the Coordinating Center

I.5.b.3. PROTOCOL VIOLATION REPORTING

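### Section I.1 assigns 25 patients per arm (50) where the rest of the protocol plans 26 per arm (52); by t-test, only 26 delivers the stated 80% power

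*Combined protocol and SAP*

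**What the plan says.** Five places agree on the total:

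- Synopsis, Number of Patients: 52.
- Synopsis, Statistical Justification: "This assumes 52 subjects (26 subjects per arm".
- G.2 Methods: "52 eligible subjects will be randomly assigned to one of two arms in a 1:1 fashion".
- H.1 Number of Subjects: "52 subjects will enter the double-blind treatment phase of the study".
- N. Data Analysis: "This assumes the randomization of 52 subjects (26 subjects per arm".

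One place differs. In I.1 Study Conduct, the text under Table 2 describes assignment at randomisation as "brexpiprazole plus intranasal ketamine (n=25) or placebo plus intranasal ketamine (n=25", which makes 50.

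Both power statements give 80% power, an effect size of 0.8 on the SDQ and a two-sided 0.05 level. Neither names the test, the scale of the SD behind the 0.8, or an expected rate of loss. J.6.a.1 says that patients who discontinue are not replaced. Section N analyses the SDQ with a linear mixed model fitted by REML to all available data, with the Day 14 difference as the primary contrast, but does not link the power calculation to that model.

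**The concern.** The Section I.1 text is current and operative. It describes how many patients are assigned to each arm, so it cannot be read as a count of completers or evaluable patients. Two totals therefore stand side by side for the same randomisation.

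The total sets the length of the randomisation list and the point at which enrolment stops. I.1.c takes each patient to "the next randomization slot from the randomization list that will have been generated by the MGH Biostatistician", and that list needs one planned size. The choice also bears on the power claim. If 26 per arm is the smallest number that reaches 80%, then 25 does not reach it, and a site or statistician working from Section I.1 would be running a trial that does not match its own justification.

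A second, smaller matter follows. If 26 is the bare minimum on complete data, a reader should be told that the 80% carries no margin for missing Day 14 values.

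**Working it through.** **Inputs from the documents.** Effect size d = 0.8; two-sided alpha 0.05; target power 80%; 1:1 allocation (Synopsis; G.2; Section N). Per-arm n = 26 (Synopsis; Section N) or 25 (Section I.1).

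**1. Reproducing the plan's figure.** For a two-sample t-test with n per arm, the noncentrality is d × √(n/2) on 2n − 2 degrees of freedom. Solving for 80% power gives n = 25.52, rounded up to 26 per arm, or 52. The plan's number reproduces, with no loss assumed.

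The normal approximation gives n = 2 × (1.960 + 0.842)² / 0.8² = 24.5, rounded up to 25 per arm, or 50. The two totals in the protocol match these two methods. That is an inference about where they came from; the documents do not say so.

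**2. Power at each number, complete data.**

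| Per arm | Noncentrality | t-test | Normal approximation |
|---|---|---|---|
| 26 | 0.8 × √13 = 2.884 | 80.7% | 82.2% |
| 25 | 0.8 × √12.5 = 2.828 | 79.1% | 80.7% |

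The t-test difference is 80.7 − 79.1 = 1.6 points. The effect detectable with 80% power moves from 0.792 (26 per arm) to 0.809 (25 per arm). With 26 in one arm and 25 in the other, t-test power is 79.95%, so on this calculation one missing value already takes it just under 80%.

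**3. Loss before Day 14.** The documents give no rate, so these rates are assumptions. The calculation is an unadjusted t-test on those remaining, from 26 per arm.

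| Assumed loss | n per arm | Power |
|---|---|---|
| 5% | 26 × 0.95 = 24.7 | 78.6% |
| 10% | 26 × 0.90 = 23.4 | 76.3% |
| 20% | 26 × 0.80 = 20.8 | 71.1% |

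**4. What the planned model may recover.** The model uses the baseline SDQ. Let r be its correlation with the Day 14 SDQ, also an assumption, with equal SDs at the two times. One degree of freedom is spent on baseline, and only patients with a Day 14 value are counted.

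- If 0.8 is in units of the raw Day 14 SD, the effective size is 0.8/√(1 − r²). For r = 0.3 to 0.5, power is 80.1% to 87.1% at 10% loss and 75.1% to 82.7% at 20%.
- If 0.8 is in change-score SD, the effective size is 0.8 × √(2/(1 + r)). For r = 0.3 to 0.7, power is 82.7% to 91.3% at 10% loss and 77.9% to 87.7% at 20%.
- If 0.8 is already baseline-adjusted, there is no further gain from baseline. Suppose a fraction m is lost after Day 11 and the Day 11–Day 14 correlation is r. The effective n is then 26/[(1 − r²)/(1 − m) + r²]. For m = 10%, r = 0.5 gives 24.0 and r = 0.8 gives 25.0, so power is 77.4% to 79.1%.

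The third case uses a different loss model from the first two, so the ranges should not be ranked against each other. Site terms and the other covariates are not modelled in any of them.

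**The case against.** The strongest reply is that this is an editorial slip. Five places agree, including both power statements, and one parenthesis differs by a single patient per arm. The stated 80% is right for 52, and a standardised effect needs no SD to reproduce the sample size. All of that stands, and it is why the point is minor. It does not remove the need to correct a wrong number in operative text.

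Four stronger readings are tempting, and the documents do not support them.

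- *The trial is underpowered.* Every loss rate and correlation above is an assumption. The unadjusted t-test is not the planned analysis, and at 10% loss both the raw-SD and change-score cases stay above 80% over the correlations tried.
- *Patients 51 and 52 would be protocol violations.* Table 5 does list "Over-enrollment", but only among the minor examples and without tying it to the Section I.1 number. I.1.c gives no length for the randomisation list.
- *The endpoint is defined in two ways.* Section E gives the outcome as "change in the SDQ total score", while Section N contrasts Day 14 values. The model treats baseline as an observation and has treatment terms only at later visits, so both arms share one baseline mean and the Day 14 difference equals the difference in change. Only the SD scale of the 0.8 is left open.
- *Discontinued patients should give a Day 14 SDQ to protect power.* That is a separate question with a trade-off. Patients who need excluded drugs are discontinued (J.5), and those removed on clinical judgment receive another treatment plan (M.7). Their later scores could reflect other treatment, yet would enter the primary contrast under the all-available-data rule. It is not part of this point.

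**Conclusion.** The conflict between 25 and 26 per arm is certain from the text. On the t-test calculation that yields 26, the Section I.1 number gives 79.1%, below the stated 80%; it reaches 80% only by the normal approximation. The size is 1.6 points of power and two patients. It does not undermine the design, and the severity is minor.

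The secondary note also holds: 26 per arm is the complete-data minimum on that calculation, with no allowance for loss and no replacement. How far power would fall in practice cannot be determined from the documents, because it depends on an unstated loss rate, an unstated SD scale and unknown correlations. The planned model may recover some or all of it.

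**What to change.** 1. Reconcile the total. If 52 is intended, change the text under Table 2 in Section I.1 to n=26 for each arm. If 50 is intended, change the Synopsis (Number of Patients and Statistical Justification), G.2, H.1 and Section N, and restate the power as 79.1% by t-test on complete data. In either case, check that the randomisation list is built to the same total.

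2. In the Synopsis justification and Section N, add one sentence saying that the 80% refers to complete Day 14 data by two-sample t-test, or name the calculation actually used if it was another. Stating the SD scale of the 0.8 there would let a reader judge how much loss the figure tolerates.

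The cost is a text amendment. The power statement may read slightly less favourably. No extra patients, visits or assessments are needed.
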